**Table 3. Adverse event definitions for reporting requirements (continued)**

Event Type	Definition
Unanticipated Serious Adverse Device Effect (USADE) (ISO14155:2011 3.42)	Serious adverse device effect which by its nature, incidence, severity or outcome has not been identified in the current version of the risk analysis report,   NOTE: Anticipated serious adverse device effect (ASADE) is an effect which by its nature, incidence, severity or outcome has been identified in the risk analysis report.
Device Deficiency	Inadequacy of a medical device with respect to its identity, quality, durability, reliability, safety or performance.   NOTE: Device deficiencies include malfunctions, use errors, and inadequate labeling.
Mandatory Problem Reporting Incident (SOR/98-282 59-61.1(2))	An incident that (a) is related to a failure of the device or a deterioration in its effectiveness, or any inadequacy in its labeling or in the directions for use, and (b) has led to the death or a serious deterioration in the state of health of a patient, user or other person, or could do so were it to recur.  NOTE: this definition and reporting requirement pertains to events that occur within Canada only.
Significant Safety Issue (SSI)  (NHMRC Safety monitoring and reporting in clinical trials involving therapeutic goods November 2016)	A safety issue that could adversely affect the safety of participants or materially impact on the continued ethical acceptability or conduct of the trial.
Urgent Safety Measure (USM)  (NHMRC Safety monitoring and reporting in clinical trials involving therapeutic goods November 2016)	A measure required to be taken in order to eliminate an immediate hazard to a participant's health or safety.  Note: This type of significant safety issue can be instigated by either the investigator or sponsor and can be implemented before seeking approval from Human Research Ethics Committees (HREC) or institutions.

### 3.3.26.2 Evaluation and Documentation of Adverse Events and Device Deficiencies

Investigators are required to evaluate and document in the subject's medical records all adverse events (AE) and device deficiencies (per the definitions in Table 4) observed in trial subjects from the time they are enrolled until they are exited from the trial. All AE should be followed through their resolution.

All AEs that occur during the trial need to be reported to Medtronic via the AE eCRF. Documented pre-existing conditions are not considered to be reportable unless there is a change in the nature or severity of the condition. Pre-existing events should be reported as AE in the situation where a new treatment has to

be started or an existing treatment has to be changed to treat the adverse event and the event is accompanied with signs and symptoms. In addition, after the subject has completed his/her two year follow-up visit, only SAE and device-related AEs need to be reported to Medtronic.

Unavoidable events are conditions which do not fulfill the definition of an Adverse Event, meaning those medical occurrences, clinical signs (including toward abnormal laboratory findings), diseases or injuries that are not untoward in nature; specifically those resulting from the intended injury such as the index SAVR or TAVR procedure. The events listed in Table 4 are expected for patients undergoing SAVR or TAVR, and do not need to be reported as AE, unless they occur outside of the stated timeframe, are otherwise considered to be an AE according to the treating investigator, or are suspected or confirmed to be device-related.

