### 3.3.3.5. Secondary Safety Endpoints

- The rate of the composite of death, disabling stroke, life-threatening bleed, major vascular complications, or AKI (II or III) at 30 days
- The rate of new permanent pacemaker implantation at 30 days
- The rate of prosthetic valve endocarditis at one year
- The rate of prosthetic valve thrombosis at one year
- The rate of all stroke (disabling and non-disabling) at one year
- The rate of life-threatening bleeding at one year
- The rate of valve-related dysfunction requiring repeat procedure at one year

The incidence estimates for each endpoint above will be provided for the two treatment groups at the specified time point. The statistical method will be the Bayesian version of a comparison of proportions (with predictions). In addition, Kaplan-Meier estimates will be provided at the following time points: 30 days, 6 months, 12 months, and annually thereafter through 10 years.

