### 3.3.26 Adverse Events, Adverse Device Effects, and Device Deficiencies

#### 3.3.26.1 Definitions

The definitions to be applied for the purposes of reporting adverse events are provided in Table 4.

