**Table 4. Adverse event definitions for reporting requirements**

Event Type	Definition
Adverse Event (AE)  (ISO14155:2011 3.2)	Any untoward medical occurrence, unintended disease or injury, or untoward clinical signs (including abnormal laboratory findings) in subjects, users or other parties, whether or not related to the investigational medical device.   NOTE 1: This definition includes events related to the investigational medical device or the comparator.  NOTE 2: This definition includes events related to the procedures involved.  NOTE 3: For users or other parties, this definition is restricted to events related to investigational medical devices.
Serious Adverse Event (SAE)  (ISO14155:2011 3.37)	Adverse event that a) led to death, b) led to a serious deterioration in the health of the subject, resulting in 1) a life-threatening illness or injury, or 2) a permanent impairment of a body structure or a body function, or 3) in-patient or prolonged hospitalization, or 4) medical or surgical intervention to prevent life-threatening illness or injury or permanent impairment to a body structure or a body function, c) led to fetal distress, fetal death or a congenital abnormality or birth defect.   NOTE: Planned hospitalization for a pre-existing condition, or a procedure required by the CIP, without serious deterioration in health, is not considered a serious adverse event.
Adverse Device Effect (ADE) or Device Related Adverse Event  (ISO14155:2011 3.1)	Adverse event related to the use of an investigational medical device.  NOTE 1: This definition includes adverse events resulting from insufficient or inadequate instructions for use, deployment, implantation, installation, or operation, or any malfunction of the investigational medical device.  NOTE 2: This definition includes any event resulting from an error use or from intentional misuse of the investigational medical device.
Serious Adverse Device Effect (SADE)  (ISO14155:2011 3.36)	Adverse device effect that has resulted in any of the consequences characteristic of a Serious Adverse Event. 

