**Table 4. Non-reportable medical occurrences associated with the index implant procedure**

Event	Timeframe (hours) from the Index Procedure
Short transient episode of arrhythmia (including ventricular fibrillation) during index procedure	0
Confusion, anxiety and/or disorientation (other than TIA/stroke) starting within 48 hours with or without medical intervention	120 (5 days)
Temporary change in mental status (other than TIA/stroke) not requiring additional medical interventions or new medical assessments (eg, CT)	72
Dizziness and/or lightheadedness with or without treatment	24
Headache with or without treatment	72
Sleep problems or insomnia with or without treatment	120 (5 days)
Mild dyspnea or cough with or without treatment	72
Oxygen supply after extubation/“forced breathing therapy”	48
Diarrhea with or without treatment	48
Obstipation/Constipation with or without treatment	72
Anesthesia-related nausea and/or vomiting with or without treatment	24
Low-grade fever (<101.3°F or <38.5°C) without confirmed infection	48
Low body temperature	6
Pain (eg, back, shoulder) related to laying on the procedure table with or without treatment	72
Incisional pain (pain at access site) with or without standard treatment and patient not returning to clinic to have additional treatment	No time limit
Pain in throat and/or trachea due to intubation	72
Mild to moderate bruising or ecchymosis	168 (7 days)
Atelectasis/Pleural Effusion not requiring punctuation	168 (7 days)
Edema resulting in weight increase up to 4 kg/9lbs from baseline	168 (7 days)

For all observed AEs, investigators should assess and document the following information on the Adverse Event eCRF:

- Date of onset or first observation
- AE code number
- Description of the event
- Seriousness of the event
- Causal relationship of the event to the TAV or surgical valve
- Causal relationship of the event to the EnVeo R DCS and/or LS
- Causal relationship of the event to the EnVeo PRO DCS and/or LS
- Causal relationship of the event to the SAVR or TAVR implant procedure
- Treatment required
- Outcome or status of the event
- Date of resolution

For all deaths, investigators should assess and document the following information on the Death and Adverse Event eCRF

- Date of death
- Primary death category
- Causal relationship of the event to the TAV or surgical valve
- Causal relationship of the event to the EnVeo R DCS and/or LS
- Causal relationship of the event to the EnVeo PRO DCS and/or LS

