### **5.4 Comparator Devices**

The comparator devices used in the SAVR control arm are any surgical aortic valve bioprostheses (stented or stentless) that are approved for commercial use in both the United States and the geography in which the study center is located. As such, the comparator devices are not investigational in this trial.

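### After the 2-year visit, the reporting rule read literally captures non-serious valve events in the TAVR arm but not in the SAVR arm, and may miss some non-disabling strokes in both

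*Protocol*

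**What the plan says.** Protocol 3.3.26.2 sets two reporting regimes. The general rule is "All AEs that occur during the trial need to be reported to Medtronic via the AE eCRF". Once a subject has completed the 2-year visit, the same paragraph narrows this: "only SAE and device-related AEs need to be reported to Medtronic".

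Section 3.3.26.1 says which definitions govern: "The definitions to be applied for the purposes of reporting adverse events are provided in Table 4". In that table the row for an adverse device effect or device-related adverse event reads "Adverse event related to the use of an investigational medical device". The row for adverse events in general is wider. Its first note says "This definition includes events related to the investigational medical device or the comparator".

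On the surgical valves, section 5.4 concludes that "the comparator devices are not investigational in this trial". Section 3.3.20 likewise lists only TAVR components as investigational.

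Section 3.3.3.5 plans Kaplan-Meier estimates of the secondary safety endpoints at "30 days, 6 months, 12 months, and annually thereafter through 10 years". SAP 6.4 also runs to 10 years. Section 3.3.27 bases the safety analysis on events that investigators report and the CEC then adjudicates.

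**The concern.** The trial is open-label, so a site knows which arm a subject is in when it decides whether an event is reportable. If *device-related* means related to the investigational system, the duty to report a non-serious valve event after 2 years depends on the randomised arm. A lower SAVR count of valve thrombosis or endocarditis in the later years could then come partly from the reporting rule.

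The loss would not show in the analysis. The CEC cannot adjudicate what it never receives. Under SAP 6.4 a subject with no recorded event is censored at the latest visit, assessment or event, so time after an unreported event counts as event-free time, not as missing data.

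A second gap does not depend on arm. An endpoint event that is neither serious nor device-related falls outside the reduced rule for everyone, although all stroke is to be estimated through 10 years.

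**Working it through.** The plan states no figure on this point, so there is none to reproduce. The check is to follow the term through the protocol and see which events remain reportable.

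1. **Governing definition.** The reduced rule (3.3.26.2) uses *device-related*. Section 3.3.26.1 sends the reader to Table 4, and Table 4 has a row under that name, limited to an investigational device.
2. **Is the limit accidental?** The same table names the comparator in the general AE row and not in the device-related row. Sections 5.4 and 3.3.20 both place the surgical valve outside the investigational devices. No sentence extends *device-related* in 3.3.26.2 to the surgical valve.
3. **Apply the rule after the 2-year visit, read literally:**

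| Event | TAVR arm | SAVR arm |
|---|---|---|
| Death, or any event meeting the SAE definition | Reported | Reported |
| Non-serious, arising from a device deficiency (3.3.26.5) | Reported | Reported |
| Non-serious, related to the implanted valve, no deficiency | Reported | Need not be reported |
| Non-serious, unrelated to any device | Need not be reported | Need not be reported |

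4. **Which planned 10-year rates this touches.** The third row bears on prosthetic valve thrombosis and endocarditis. The fourth bears on all stroke. Appendix V defines a non-disabling stroke by a 90-day mRS below 2, or by no rise of at least one category from the pre-stroke baseline. Such a stroke, if it leaves no permanent impairment, does not lead to or prolong a hospital stay, and meets no other SAE criterion, is non-serious.
5. **What it does not touch.** Valve dysfunction is taken from the echo core lab in both arms (Appendix V, section 3.0, note 4). Repeat procedures have their own eCRFs (Appendix V, section 1.0). The primary endpoint is at 24 months, the secondary safety endpoints are defined at 30 days or 1 year, and all the secondary tests in the hierarchy (3.3.3.7) use data from 1 year or earlier. All of these precede the change of rule.
6. **Length of the period.** 10 − 2 = 8 years, or 8/10 = 80% of planned follow-up, falls under the reduced rule.
7. **Size.** If a share *s* of a given valve event is non-serious and every site follows the literal rule, the SAVR arm records a fraction 1 − *s* of its events after year 2, while the TAVR arm records all of them. The direction follows from the rule. The documents give neither *s* nor the proportion of sites that would read the rule literally, so no number follows.

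**The case against.** The strongest reply is that the term is ambiguous and that sites may not read it narrowly. The paragraph after the reduced rule uses *device-related* when speaking of subjects having either SAVR or TAVR. The AE form has a single field, "Causal relationship of the event to the TAV or surgical valve", and Appendix V section 5.0 gives causality guidance covering both valve types. A site completing that form could well treat a surgical-valve event as device-related. This stands as a limit on the point: the literal reading is available and nothing overrides it, but it is not the only reading. The causality field describes an event once it is entered and does not create the duty to enter it. If sites read the rule differently, capture varies by site, which also needs correcting.

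Other passages carry no 2-year limit. Section 3.3.14 has adverse events documented at each follow-up, 3.3.17 provides forms for unscheduled contacts about possible endpoint events, and 3.3.26.2 asks for source documents on all endpoint-related events. These soften the gap, but none says that it displaces the word *only* in the reduced rule. The Safety Plan and CEC charter, which might settle the matter, are not among the documents.

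Many of the events in question will be serious. The SAE definition includes treatment given to prevent life-threatening illness or permanent impairment, without requiring admission, so a treated valve thrombosis will often qualify. Possible endocarditis is coded separately from definite, and the documents do not say whether it counts towards the endpoint. This narrows the affected group without emptying it.

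The reduction in reporting was deliberate: the protocol's version history lists it under version 1C. The same version lists the 10-year rates of endocarditis, thrombosis and all stroke, so intent does not resolve the mismatch between the two.

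**Conclusion.** The point holds as a wording gap with a predictable direction. Under the protocol's own definitions, after 2 years a non-serious surgical-valve event need not be reported while the same transcatheter-valve event must be. Some non-serious endpoint events may also be lost in both arms. The conclusion rests on sites applying the governing definition as written. Where they do, recorded SAVR valve events will be too few relative to TAVR, and all-stroke rates after year 2 may be too low in both arms.

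Three stronger readings are tempting and the documents do not support them.

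- A reader might infer that the long-term comparison of valve durability is biased. Valve dysfunction and repeat procedures, which carry most of that comparison, do not depend on this rule.
- A reader might want to state a spurious TAVR-to-SAVR ratio. Any such ratio restates the assumed non-serious share, for which the documents give no figure. The planned Kaplan-Meier estimates also include two fully reported years, which dilutes it.
- A reader might think the trial's conclusions are at risk. Sample size, power and type I error are untouched, and no formal test of the affected endpoints is specified after year 2.

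This is a cheap improvement to descriptive safety data that span 8 of the 10 years of follow-up.

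**What to change.** Replace the sentence in Protocol 3.3.26.2 with one that applies equally to both arms. After the 2-year visit and through 10 years, sites report:

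- all SAEs;
- all AEs judged at least possibly related to the TAV, its delivery system or the surgical valve; and
- every event meeting the definition of a safety endpoint that is to be estimated through 10 years, whatever its seriousness or relatedness.

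Carry the same wording into the eCRF guidance. While the text is open, correct the table numbers: Table 4 labels both the event definitions and the list of non-reportable occurrences, and the definitions continue under the label Table 3.

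The cost is a few more AE forms per site. Adverse events are already reviewed every year, by telephone in years 6, 8 and 9, and the causality field already covers both valve types. The change is best made early, because non-serious events not collected at the time may be hard to recover later.

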**Table 4. Non-reportable medical occurrences associated with the index implant procedure**

Event	Timeframe (hours) from the Index Procedure
Short transient episode of arrhythmia (including ventricular fibrillation) during index procedure	0
Confusion, anxiety and/or disorientation (other than TIA/stroke) starting within 48 hours with or without medical intervention	120 (5 days)
Temporary change in mental status (other than TIA/stroke) not requiring additional medical interventions or new medical assessments (eg, CT)	72
Dizziness and/or lightheadedness with or without treatment	24
Headache with or without treatment	72
Sleep problems or insomnia with or without treatment	120 (5 days)
Mild dyspnea or cough with or without treatment	72
Oxygen supply after extubation/“forced breathing therapy”	48
Diarrhea with or without treatment	48
Obstipation/Constipation with or without treatment	72
Anesthesia-related nausea and/or vomiting with or without treatment	24
Low-grade fever (<101.3°F or <38.5°C) without confirmed infection	48
Low body temperature	6
Pain (eg, back, shoulder) related to laying on the procedure table with or without treatment	72
Incisional pain (pain at access site) with or without standard treatment and patient not returning to clinic to have additional treatment	No time limit
Pain in throat and/or trachea due to intubation	72
Mild to moderate bruising or ecchymosis	168 (7 days)
Atelectasis/Pleural Effusion not requiring punctuation	168 (7 days)
Edema resulting in weight increase up to 4 kg/9lbs from baseline	168 (7 days)

For all observed AEs, investigators should assess and document the following information on the Adverse Event eCRF:

- Date of onset or first observation
- AE code number
- Description of the event
- Seriousness of the event
- Causal relationship of the event to the TAV or surgical valve
- Causal relationship of the event to the EnVeo R DCS and/or LS
- Causal relationship of the event to the EnVeo PRO DCS and/or LS
- Causal relationship of the event to the SAVR or TAVR implant procedure
- Treatment required
- Outcome or status of the event
- Date of resolution

For all deaths, investigators should assess and document the following information on the Death and Adverse Event eCRF

- Date of death
- Primary death category
- Causal relationship of the event to the TAV or surgical valve
- Causal relationship of the event to the EnVeo R DCS and/or LS
- Causal relationship of the event to the EnVeo PRO DCS and/or LS
- Causal relationship of the event to the implant procedure

In addition, for all endpoint-related adverse events and deaths, sites should submit relevant, de-identified source documents to Medtronic for the Clinical Events Committee (CEC) members to use in their adjudication of the event. The CEC may request source documentation on additional events, at their discretion and according to the CEC Charter.

Definitions of safety endpoints, the AE code list, and guidelines for accessing causal relationships are provided in APPENDIX V: DEFINITIONS: SAFETY ENDPOINTS AND EFFICACY EVENTS.

### **3.3.26.3 Anticipated Adverse Events**

Adverse events that are anticipated for subjects participating in this trial are described in Section 4.2, Risks.

### 3.3.26.4 Adverse Event Reporting Requirements for Clinical Sites

Adverse events and device deficiencies that occur during this trial are required to be reported to Medtronic via the AE or device deficiency eCRF, as soon as possible after the event occurs, but no later than the timeframes listed in Table 5 or local requirements, whichever is more stringent.

**Table 5. Required timeframes for adverse event reporting to Medtronic**

Event Type	Timeframe for Reporting
Adverse Event (AE)	No later than 10 working days of the investigator's/site's first knowledge of the event
Serious Adverse Event (SAE)	Immediately, but no later than 72 hours of the investigator's/site's first knowledge of the event
Adverse Device Effect (ADE) or Device Related Adverse Event	Immediately, but no later than 72 hours of the investigator's/site's first knowledge of the event
Serious Adverse Device Effect (SADE)	Immediately, but no later than 72 hours of the investigator's/site's first knowledge of the event
Unanticipated Adverse Device Effect (UADE)	Immediately, but no later than 72 hours of the investigator's/site's first knowledge of the event
Unanticipated Serious Adverse Device Effect (USADE)	Immediately, but no later than 72 hours of the investigator's/site's first knowledge of the event
Device Deficiency	No later than 72 hours of the investigator's/site's first knowledge of the event
Device Deficiency that might have led to a SADE	Immediately, but no later than 72 hours of the investigator's/site's first knowledge of the event
Additional event types	Additional Time Frame for Reporting
Mandatory Problem Reporting Incident (Canada ONLY)	No later than 72 hours of the investigator's/site's first knowledge of the event, to Health Canada
Significant Safety Issue (SSI) (Australia ONLY)	No later than 72 hours of the investigator's/site's first knowledge of the event
Urgent Safety Measure (USM) (Australia ONLY)	Immediately, but no later than 24 hours of the investigator's/site's first knowledge of the event

In addition, Investigators are obligated to report adverse events in accordance with the requirements of their reviewing IRB/EC and local regulations.

The Sponsor is obligated to report adverse events and device deficiencies that occur during this trial to the Regulatory Authorities and IRB/EC as per local requirements. The applicable timeframes are described in the Safety Plan associated with this trial.

